#### 13.8.4 Sensitivity Analysis

Sensitivity analyses will be explored for reasoning expressed in both Sections 13.1 and 13.7 above. The first sensitivity analysis will attempt to identify the direction and magnitude of the bias resulting from the availability of clinical BG and GM testing outside of the ancillary study. Such testing has the potential to change the treating clinician's approach for diagnosing an IFI. It is possible that these test results could result in more or less investigation (i.e., radiologic imaging) to identify an IFI which could ultimately impact on the incidence of identified IFI. Therefore, in addition to calculating the operating characteristics for all patients enrolled as described in Section 13.8.2 above, the same operating characteristics will be calculated after excluding all patients that had at least 1 biomarker test result available to the treating clinician.

The second sensitivity analysis will be performed to explore the impact of the various factors described in Section 13.7 that may contribute to a positive result for either biomarker. False positive results would impact the final interpretation of sensitivity and PPV for each of the assays. However, it is also possible that one of the factors listed in Table 3 is present in a patient that truly has an IFI. Therefore, we plan to still include all patients in the primary analysis for calculation of each assays' operating characteristics. In this sensitivity analysis, we will eliminate all patients with a positive test that correlates in time with at least 1 of the factors listed in Table 3.

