### 13.7 Factors resulting in False Positive Results

A number of medications, medical interventions, and infections have been suggested as possible causes of false positive results for BG and GM testing. Table 3 lists the potential causes of false positive results reported in the literature. It is anticipated that patients being treated for AML will have reason to be exposed to a number of these medications, infusions and/or medical interventions. Additionally, *Pneumocystis jiroveci* infection is also considered a cause of a “false positive” BG test. Technically this is not a true false positive as the Fungitell Assay is detecting BG from the cell wall of *Pneumocystis jiroveci* as it would for other fungal infections. However, in this instance it is considered a false positive as the treatment of choice for this infection is trimethoprim-sulfamethoxazole as opposed to a typical anti-fungal agent. A sensitivity analysis (as described in Section 13.8.4 below) will be performed to investigate the impact of these false positive rates on the operating characteristics of the 2 biomarkers.

**Table 3.** Potential factors resulting in false positive testing for (1→3) beta-D glucan and GM assays

Factor	(1→3) Beta-D Glucan Assay	Galactomannan EIA Assays
Medications	Amoxicillin-clavulanate	*Piperacillin-Tazobactam *Amoxicillin-clavulanate
Infusions	*Intravenous immune globulin *Cellulose filters for IV infusion *Albumin	*Plasmalyte (electrolyte infusion) *Intravenous solution with sodium gluconate
Medical interventions	*Hemodialysis with cellulose filter *Gauze packing on serosal surfaces	*Enteral feeding with soybean proteins
Other infections	* Pneumocystis jiroveci	* Penicillium spp. * Histoplasma capsulatum * Geotrichum * Neosartoria

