#### 13.8.2 Sensitivity, Specificity, PPV, and NPV

The validity of a biomarker is based on whether the study appropriately categorizes patients with and without the illness in question (sensitivity and specificity). Alternatively the validity of a test can be measured by how well the test results predict the presence or absence of the disease (PPV and NPV). Collectively, sensitivity, specificity, PPV, and NPV are often referred to as the test's operating characteristics with the sensitivity and NPV being the most clinically relevant parameters for this study. Each component of the operating characteristics will be calculated based first on the entire cohort. As indicated in the sample size estimates above the incidence of IFI will vary between the two study arms. It is well documented that variations in the incidence/prevalence of a disease will impact the operating characteristics of a diagnostic test specifically for the PPV and NPV. Therefore, each assay's sensitivity, specificity, PPV and NPV will also be calculated separately for each study arm.

The operating characteristics for both the Platelia *Aspergillus* EIA and the Fungitell Assay will be computed at the patient level for each of the sub-aims as follows:

- a) Outcome of IA only **or** all IFI defined as a single positive test for either the Platelia *Aspergillus* EIA **or** the Fungitell Assay as compared to the EORTC/MSG criteria for proven or probable IA only **or** all IFI.
- b) Outcome of IA only defined as a single positive test for Platelia *Aspergillus* EIA only as compared to the EORTC/MSG criteria for proven or probable IA only.
- c) Outcome of all IFI defined as a single positive test for the Fungitell Assay as compared to the EORTC/MSG criteria for all proven or probable IFI.

Sensitivity, specificity, PPV and NPV and their accompanying 95% confidence intervals will be calculated using STATA statistical software version 11.0 (College Station, TX). As noted above, these parameters will first be calculated for the entire cohort and then for each study arm separately. The latter analyses are important as the incidence of IFI may vary by study arm thus impacting the interpretation of the assay results. A patient with multiple episodes of IFI will only be included in the analyses as a single IFI.

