**APPENDIX II: EORTC/MSG CRITERIA**

**Criteria for proven invasive fungal disease except for endemic mycoses**

Analysis and specimen	Molds a	Yeasts a
Microscopic analysis: sterile material	Histopathologic, cytopathologic, or direct microscopic examination b of a specimen obtained by needle aspiration or biopsy in which hyphae or melanized yeast-like forms are seen accompanied by evidence of associated tissue damage	Histopathologic, cytopathologic, or direct microscopic examination b of a specimen obtained by needle aspiration or biopsy from a normally sterile site (other than mucous membranes) showing yeast cells—for example, Cryptococcus species indicated by encapsulated budding yeasts or Candida species showing pseudohyphae or true hyphae c
Culture		
Sterile material	Recovery of a mold or “black yeast” by culture of a specimen obtained by a sterile procedure from a normally sterile and clinically or radiologically abnormal site consistent with an infectious disease process, excluding bronchoalveolar lavage fluid, a cranial sinus cavity specimen, and urine	Recovery of a yeast by culture of a sample obtained by a sterile procedure (including a freshly placed [!24 h ago] drain) from a normally sterile site showing a clinical or radiological abnormality consistent with an infectious disease process
Blood	Blood culture that yields a mold d (e.g., Fusarium species) in the context of a compatible infectious disease process	Blood culture that yields yeast (e.g., Cryptococcus or Candida species) or yeast-like fungi (e.g., Trichosporon species)
Serological analysis: CSF	Not applicable	Cryptococcal antigen in CSF indicates disseminated cryptococcosis

a If culture is available, append the identification at the genus or species level from the culture results.

b Tissue and cells submitted for histopathologic or cytopathologic studies should be stained by Grocott-Gomori methenamine silver stain or by periodic acid Schiff stain, to facilitate inspection of fungal structures. Whenever possible, wet mounts of specimens from foci related to invasive fungal disease should be stained with a fluorescent dye (e.g., calcofluor or blankophor).

c *Candida*, *Trichosporon*, and yeast-like *Geotrichum* species and *Blastoschizomyces capitatus* may also form pseudohyphae or true hyphae.

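### The false-positive sensitivity analysis in 13.8.4 names sensitivity where specificity is meant, and its exclusion rule can delete true positives but never false negatives

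*Combined protocol and SAP*

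**What the plan says.** Section 13.7 lists, in Table 3, medications, infusions, interventions and infections that may cause a false-positive beta-D glucan or galactomannan (GM) result, with one column per assay. It announces a sensitivity analysis to "investigate the impact of these false positive rates on the operating characteristics of the 2 biomarkers". Section 13.8.2 defines that term: "Collectively, sensitivity, specificity, PPV, and NPV are often referred to as the test's operating characteristics". It also singles out two of the four, "with the sensitivity and NPV being the most clinically relevant parameters for this study".

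Section 13.8.4 gives the rationale for the analysis: "False positive results would impact the final interpretation of sensitivity and PPV for each of the assays". It then recognises that "it is also possible that one of the factors listed in Table 3 is present in a patient that truly has an IFI", and for that reason keeps all patients in the primary analysis. For the sensitivity analysis itself the rule is: "we will eliminate all patients with a positive test that correlates in time with at least 1 of the factors listed in Table 3".

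Section 13.8.1 leaves only Zygomycetes and Cryptococci out of the IFIs that count as true events for Fungitell, and counts only invasive aspergillosis (IA) for the GM assay. In Appendix II, a footnote to the yeast microscopy criterion for proven disease notes that "yeast-like *Geotrichum* species and *Blastoschizomyces capitatus* may also form pseudohyphae or true hyphae".

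**The concern.** A false positive is a positive test in a patient without the disease, so it belongs to specificity and PPV. The rationale names sensitivity and PPV and omits specificity. Because 13.8.2 already puts sensitivity first among the clinically relevant measures, a reader of the results would naturally look there for the effect of drugs and infusions.

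The exclusion rule makes that reading misleading. It conditions on the test result: patients with a factor and a positive test leave, while patients with the same factor and a negative test stay. Any fall in sensitivity would come from the deletion of detected cases, yet the rationale invites the reader to attribute it to false positives.

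The rule also refers to Table 3 as a whole, not to the column for the assay analysed. Taken literally, a Fungitell-positive patient would be dropped for a factor listed only under GM, such as piperacillin-tazobactam. Some listed factors are fungal infections. Where the outcome is all IFI, a correctly detected infection of that kind could be removed as though it were a false alarm.

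**Working it through.** **Definitions.** Sensitivity = TP/(TP+FN); specificity = TN/(TN+FP); PPV = TP/(TP+FP); NPV = TN/(TN+FN).

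**The plan's own figures.** Table 1 in 13.2.3.2 follows these definitions. Specificity is 55/63 = 87.3%, 82/88 = 93.2%, 304/338 = 89.9% and 25/27 = 92.6%, all as printed. In the 347-patient study, 34 false positives lower specificity to 89.9% while sensitivity is 9/9 = 100%. The event counts in 13.8.1 also reproduce: 220 × 0.08 = 17.6, rounded to 18, and 220 × 0.02 = 4.4, rounded to 4, giving 22 IFI among 440 patients.

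**Illustrative inputs.**
- 22 IFI and 440 − 22 = 418 patients without IFI (13.8.1).
- 20 detected and 2 missed. This is an assumption, chosen near the 90% hypothesis in 13.3.
- 15% false positives, the share of healthy children at or above 80 pg/mL cited in 13.6.1.1: 418 × 0.15 ≈ 63, leaving 355 true negatives. Applying it here is an assumption; step 1 shows a range.
- The share of positives with a Table 3 factor. The documents give none, so several are shown.

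**Step 1: change only the number of false positives.** Over 0, 21, 42, 63, 84 and 125, specificity is 100, 95.0, 90.0, 84.9, 79.9 and 70.1%, and PPV is 100, 48.8, 32.3, 24.1, 19.2 and 13.8%. Sensitivity is 20/22 = 90.9% throughout.

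**Step 2: apply the planned rule.** FN = 2 and TN = 355 never change, so NPV stays at 355/357 = 99.4%.

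| Removed | TP | FP | Sensitivity | Specificity | PPV |
|---|---|---|---|---|---|
| None | 20 | 63 | 20/22 = 90.9% | 355/418 = 84.9% | 20/83 = 24.1% |
| 25% of all positives | 15 | 47.25 | 15/17 = 88.2% | 355/402.25 = 88.3% | 24.1% |
| 50% of all positives | 10 | 31.5 | 10/12 = 83.3% | 355/386.5 = 91.8% | 24.1% |
| 75% of all positives | 5 | 15.75 | 5/7 = 71.4% | 355/370.75 = 95.8% | 24.1% |
| 50% of FP only | 20 | 31.5 | 90.9% | 91.8% | 20/51.5 = 38.8% |
| 50% of TP, 25% of FP | 10 | 47.25 | 83.3% | 88.3% | 10/57.25 = 17.5% |

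Sensitivity and specificity each move in only one direction. PPV can stay, rise or fall, depending on the mix of true and false positives removed.

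**Step 3: listed infections.** For GM against IA only, the organisms in the GM column are not Aspergillus, so none is a target case. For an all-IFI outcome (Fungitell, or either test positive), 13.8.1 does not exclude Geotrichum or Penicillium from the true events, and the proven-yeast criterion contemplates Geotrichum. Removing 1, 2 or 3 such true positives gives 19/21 = 90.5%, 18/20 = 90.0% or 17/19 = 89.5%.

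**The case against.** **Specificity is not left out.** A reader might infer that the whole analysis is aimed at the wrong measure and that specificity would go unreported. The documents do not support that. Section 13.7 sets the scope as the operating characteristics, and 13.8.2 defines these to include specificity. The error is in the rationale sentence.

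**Sensitivity has a coherent role.** Analysis is by patient, and one positive test suffices. A positive caused by a drug in a patient who also has an IFI is scored as a true positive and inflates sensitivity; 13.8.4 raises this overlap itself. That stands as a possible intention, but such a result is not a false positive in the table, and the rule does not correct it. If one of 20 detections were coincidental, the corrected figure would be 19/22 = 86.4%; deleting the patient gives 19/21 = 90.5%.

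**The main estimates are protected.** A reader might infer that the deletions threaten the hypotheses of sensitivity above 90%. They do not: the primary analysis deletes nobody, and 13.8.2 plans estimates with confidence intervals, not a pass/fail test at 90%. The exact 95% interval for 20/22 runs from 70.8% to 98.9%, far wider than the shifts in step 3.

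**The infection point is narrow.** Geotrichum, Penicillium and Histoplasma appear only in the GM column, so a rule applied by assay would not reach them for Fungitell alone. *P. jiroveci* is a deliberate choice explained in 13.7. Appendix II's tables exclude endemic mycoses, so the status of Histoplasma cannot be settled from the documents. Section 2.1 attributes IFI in these children mainly to Candida and Aspergillus, so even two or three such cases among 22 would be unlikely. All of this stands as a limit on size. It does not repair the rule for the either-test, all-IFI outcome.

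**Conclusion.** The concern holds in a limited form. The rationale in 13.8.4 names the wrong measure: false positives bear on specificity and PPV. Separately, the exclusion rule depends on the test result, so it can only lower or hold sensitivity and only raise or hold specificity, whatever the assays' true performance.

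The size depends on how many positives carry a factor, which the documents do not say. With the assumed 20 of 22 detected and 63 false positives, removing 25% to 75% of all positives takes sensitivity to between 88.2% and 71.4% with PPV unchanged. The loss of true IFIs through the infection row arises only for all-IFI outcomes under the literal rule, and is probably small.

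The randomised comparison, the primary biomarker estimates and GM against IA as regards the infection row are not affected. This is a planned secondary analysis of an optional ancillary study whose results would be misread as written.

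**What to change.** In 13.8.4:

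1. In the rationale, replace sensitivity and PPV with specificity and PPV, and make these the stated results of the second sensitivity analysis.
2. State that any change in sensitivity in this analysis reflects removed true positives and is not an effect of false positives.
3. Apply each Table 3 factor only to the assay under which it is listed.
4. Keep patients whose listed infection is itself a proven or probable event for the outcome analysed. This is still needed after item 3, because the either-test rule uses both columns. The choice on *P. jiroveci* in 13.7 can stand if it is restated here.
5. Report the numbers of true and false positives removed separately, since PPV alone does not show the mix.

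The cost is wording in the analysis plan; no change to sampling, testing or the primary biomarker analysis is needed. An optional addition would exclude on exposure regardless of test result, which removes the asymmetry. Section 7.2.1 already records exposure or its absence for amoxicillin-clavulanate, piperacillin-tazobactam and intravenous immunoglobulin in each neutropenic period, so this would be feasible at least for those three.

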### 13.4 Patient Accrual

All patients enrolled on ACCL0933 will be offered the chance to participate in the anti-fungal screening study. We anticipate that at least 80% of the patients in the parent trial will enroll in this ancillary study resulting in an estimated 440 patients at baseline. Those who consent will undergo Platelia *Aspergillus* EIA and Fungitell Assay testing. Blood sampling will be conducted twice weekly during anti-fungal prophylaxis treatment after each course of chemotherapy.

Each patient will have the potential for multiple courses of chemotherapy with each course having variable durations of neutropenia. Based on data from the AAML0531 trial, we have estimated the number of patients progressing from the first course of chemotherapy through the fourth course of therapy as well as duration of neutropenia for each course (see Table 2). Given a planned frequency of biomarker testing of twice per week, estimates of the number of Platelia *Aspergillus* EIA and Fungitell Assays performed during each chemotherapy course are provided (see Table 2).

**Table 2.** Estimated number of Platelia *Aspergillus* EIA and Fungitell Assay performed per course.

Chemotherapy course	Estimated Duration of neutropenia* (days)	# of testing time points for 1 patient during neutropenia †	Platelia EIA	Fungitell Assay
I (n=440)	20	6	2640	2640
II (n=380)	18	5	1900	1900
III (n=337)	17	5	1685	1685
IV (n=216)	28	8	1728	1728
Total	-	-	7953	7953

\*Based on median duration of neutropenia for each course from AAML0531 trial

†Based on a plan for 2 tests per week during neutropenic period

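### The false-positive sensitivity analysis in 13.8.4 excludes patients by test result, so within an assay specificity can only rise or stay and sensitivity can only fall or stay, even for a harmless factor

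*Combined protocol and SAP*

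**What the plan says.** Section 13.7 lists in Table 3 the drugs, infusions, procedures and infections reported to cause false positives on the beta-D glucan (Fungitell) and galactomannan (GM, Platelia) assays. It says of the AML population: "It is anticipated that patients being treated for AML will have reason to be exposed to a number of these medications". It adds that a sensitivity analysis "will be performed to investigate the impact of these false positive rates on the operating characteristics of the 2 biomarkers".

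Section 13.8.4 gives the rule: "we will eliminate all patients with a positive test that correlates in time with at least 1 of the factors listed in Table 3". The reason offered is: "False positive results would impact the final interpretation of sensitivity and PPV for each of the assays". The same paragraph notes that a listed factor may be present in a patient who truly has an IFI, and it keeps all patients in the primary analysis.

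Section 13.8.2 works at patient level. For glucan the rule is "Outcome of all IFI defined as a single positive test for the Fungitell Assay". The combined outcome is "defined as a single positive test for either the Platelia" assay or the Fungitell assay. Section 7.2.1 requires exposure or its absence to be recorded in each neutropenic period for amoxicillin-clavulanate, piperacillin-tazobactam and intravenous immunoglobulin.

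**The concern.** The exclusion depends on the outcome being evaluated. A patient exposed to, say, piperacillin-tazobactam leaves the table if the test was positive and stays if it was negative. Removing only positives improves specificity and lowers sensitivity mechanically, whether or not the drug caused any of them.

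Section 13.7 relies on this analysis to show what the factors do to the assays. A factor with no effect would look as if it had been depressing specificity. A loss of sensitivity produced by the exclusion could also be set against the target of more than 90% in section 13.3. In addition, the stated rationale leaves out specificity, the measure that false positives affect most directly.

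**Working it through.** **Inputs.** From 13.8.1: 220 patients per arm, 440 in all. Expected IFI are 220 × 0.08 = 17.6 (stated as 18) and 220 × 0.02 = 4.4 (stated as 4). That makes 22 IFI and 418 patients without IFI, and the plan's counts reproduce. Assumed: sensitivity s = 0.90 and specificity p = 0.90. The share e of positive patients whose positive coincides with a factor is also assumed. The documents give no figure for it, so a range is shown.

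**Direction.** Let the rule remove a true positives and b false positives from one assay's table. False negatives (FN) and true negatives (TN) are untouched.
- Sensitivity becomes (TP − a)/(TP − a + FN), which is at most TP/(TP + FN).
- Specificity becomes TN/(TN + FP − b), which is at least TN/(TN + FP).
- NPV = TN/(TN + FN) does not change.

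Enumeration of 836,550 small tables found no exception. In the combined table a positive on either assay makes the patient positive, so the result holds there under any reading.

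**Size for a harmless factor.** Sensitivity = s(1 − e)/[s(1 − e) + 1 − s]; specificity = p/[p + (1 − p)(1 − e)].

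| e | Sensitivity | Specificity |
|---|---|---|
| 0 | 90.0% | 90.0% |
| 10% | 0.81/0.91 = 89.0% | 0.90/0.99 = 90.9% |
| 50% | 0.45/0.55 = 81.8% | 0.90/0.95 = 94.7% |

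PPV stays at 19.8/61.6 = 32.1% and NPV at 376.2/378.4 = 99.4%.

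**A harmful factor can give the same specificity shift.** Let 20% be exposed, with specificity 75% in them and 93.75% in the rest. The primary value is 0.2 × 0.75 + 0.8 × 0.9375 = 90%. The rule leaves false positives of 0.8 × 0.0625 = 5%, so specificity is 0.90/0.95 = 94.7%, as for the harmless factor at e = 50%.

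**PPV separates these two cases, but not in general.** With equal IFI risk and sensitivity in both groups, the harmful factor moves PPV from 32.1% to 15.84/(15.84 + 20.9) = 43.1%. Now take a harmless factor in half the patients, with IFI risk 7.5% in the exposed (16.5 of 220) and 2.5% in the rest (5.5 of 220). PPV falls from 32.1% to 4.95/(4.95 + 21.45) = 18.8% with no effect of the factor at all.

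**Will sensitivity fall in practice?** It falls if at least one IFI patient is missed and at least one detected IFI patient is removed. The probability is 1 − sⁿ − (1 − se)ⁿ + [s(1 − e)]ⁿ. With n = 22 IFI it is 79% at e = 10% and 90% at e = 50%. With the 7 to 8 invasive aspergillosis cases expected, it is 23% to 28% and 51% to 56%.

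**Does a split by exposure behave better?** Table 2 in 13.4 implies that 60, 43, 121 and 216 patients stop after one to four courses, with 6, 11, 16 and 24 tests. Assume independent tests, patient-level specificity of 90% (per-test specificity 99.41%) and exposure drawn independently in half of courses.

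| Specificity | Harmless factor | Per-test false-positive risk tripled by exposure |
|---|---|---|
| Planned rule, before and after | 90.0% to 94.8% | 81.2% to 94.7% |
| By course, unexposed v exposed | 96.7% v 96.7% | 96.7% v 90.3% |

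A crude patient-level split for the harmless factor gives 93.0% unexposed v 89.4% exposed. That spurious 3.6 points arises because patients with more courses have both more tests and more chances of exposure. Hence the adjustment for number of tests in the remedy.

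**The case against.** **The primary analysis keeps everyone, and this check is exploratory.** That is correct. It limits the consequence but does not make the check interpretable.

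**It can be read as a bounding scenario.** Table 3 lists factors already reported to cause false positives, so discarding coincident positives as uninterpretable is a possible exercise. The text does not describe it that way; 13.7 says it investigates the factors' impact.

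**The direction is not fixed everywhere.** This stands. A reader might infer that it is fixed in every table, but 13.8.4 does not say whether a positive on one assay also removes the patient from the other assay's table. If it does, that other table can move either way. The same applies at the other cutoffs or under the two-consecutive-positives rule of 13.8.3, where a removed patient may have counted as negative.

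**Naming sensitivity is defensible.** This also stands. A reader might infer that false positives have nothing to do with sensitivity. At patient level, a factor-induced positive in a patient with IFI counts as a true positive. For example, 80% true detection plus induced positives in an independent 20% of IFI patients gives 1 − 0.2 × 0.8 = 84%. The fault is the omission of specificity.

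**The size is unanchored.** Fair. At 10% coincidence the shifts are about one point.

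**Conclusion.** The concern holds within stated limits. Under the single-positive, patient-level definition, assay by assay and in the combined table under any reading, the direction of change in sensitivity and specificity is set by the exclusion rule and NPV cannot move. That is algebra and needs no assumed rates. The size does depend on assumptions: about 1 point on each measure at 10% coincidence, and 8.2 points down in sensitivity with 4.7 up in specificity at 50%. PPV is informative only if IFI risk is similar in exposed and unexposed patients.

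Two stronger conclusions are not supported. One is that the specificity shift never carries information. With half exposed and specificity 70% v 90%, it goes from 80% to 0.80/0.85 = 94.1%, whereas a harmless factor from the same start would give 0.80/0.90 = 88.9%. Telling these apart requires the exposure share among test-negative patients, which the planned rule does not use. The other is that the biomarker results as a whole are biased: the primary operating characteristics include all patients, and the treatment comparison does not depend on this check. The severity is minor.

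**What to change.** Replace exclusion by test result with a comparison by exposure. Suggested wording for 13.8.4:

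*For each assay, patients will be classed as exposed or unexposed to the recorded factors in that assay's column of Table 3, whatever their test results; either column applies for the combined table. Sensitivity, specificity and PPV will be reported at patient level in each group, with the proportion who have an IFI and with adjustment for the number of tests. Specificity is the lead comparison.*

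Further points:
- Use the three agents for which 7.2.1 records exposure or its absence. They cover two of seven entries in the glucan column and two of nine in the GM column. The listed infections rest on microbiology, pathology and adverse event reports.
- A split by neutropenic period, with intervals clustered by patient, may be added for specificity among patients who never have an IFI. Used more widely it would need an IFI status for each period, which the plan does not define.
- If the planned exclusion is kept, label it a bounding scenario whose direction is known in advance, and state that exclusion for one assay does not remove the patient from the other assay's table.
- In the rationale, add specificity beside sensitivity and PPV.

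**Cost.** A wording change, with no new data for the three agents. Sensitivity by group will be imprecise: 10 of 11 IFI detected has an exact 95% interval of 58.7% to 99.8%. Exposure is not randomised, so differences are descriptive. Power falls if nearly everyone is exposed. For 80% v 90% specificity it is about 82% with 209 v 209 patients, but only about 31% to 53%, depending on the form of test, with 376 v 42.
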